**Table 4 - Schedule of PK Sample Collection**

Ideal timing of PK sample collection	Acceptable leeway
D1: before intake of IP	
D1: 4 hours after intake of IP	± 1 hour
D1: 9 hours after intake of IP	± 1 hour
D2: 24 hours after intake of IP	± 1 hour
D3: 48 hours after intake of IP	± 1 hour
D4: 72 hours after intake of IP	± 1 hour
D5: 96 hours after intake of IP	± 1 hour
D11: 240 hours after intake of IP	± 1 hour

- The timepoints for sampling were chosen in order to best predict the concentrations of acoziborole during the absorption and elimination phases.

Lumbar puncture will be performed on Day 11, 240 hours after the intake of acoziborole, and the CSF sample will be used for initial assessment of the treatment effect, based on WBC and screening for trypanosomes, as well as for assays of acoziborole. The samples will be destroyed at the latest once the final

study report has been validated and signed. The destruction procedure will be recorded in a certificate of destruction.

The blood and CSF samples collected on filter paper will be stored at room temperature (see Laboratory Manual).

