**Table 5 - Populations Used in the Analyses**

Type	Aim	Definition
Primary: modified intent-to-treat (mITT) patients	Primary analysis	All patients who received at least one tablet of acoziborole, excluding patients who fled the region due to armed conflict or natural disaster, or due to force majeure, and for whom no post-treatment data are available. These patients will be included in the population as failures for an “all-patient” sensitivity analysis.
All patients	Safety analyses and sensitivity analyses on efficacy	All patients who received at least one tablet of acoziborole. There will be no exceptions to this rule.
Secondary: evaluable patients	Sensitivity analyses on efficacy	Patients in the mITT population for whom at least one lumbar puncture is available (at 6, 12 or 18 months), and excluding patients who died for reasons clearly unrelated to efficacy or safety, or who fled the region due to armed conflict or natural disaster.
Secondary: per-protocol patients	Sensitivity analyses on efficacy	Patients in the mITT population with no major protocol violations. Major violations will be described by patient, and exclusion will be decided during the data review.

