## 5. ANALYSIS SETS AND SUBGROUPS

The analysis sets are defined below:

- **Set of screened HAT positive patients:** All HAT positive patients who signed the informed consent. To be noted that after the 1st DSMB meeting, recruitment of stage 1 and intermediate stage HAT patients was authorized. That will trigger a modification of the initial screened set.
- **Treated set:** all patients who received at least one tablet of acoziborole.
- **Modified Intention-To-Treat (mITT):** All patients who received at least one tablet of acoziborole, excluding patients (\*) who fled the region due to armed conflict or natural disaster or due to force majeure (\*\*) and for whom no failure was detected early (parasite, needs for rescue medication, death or more than 50 WBC/µL in CSF at M6) and no data are available at M12 and M18 due to armed conflict, natural disaster or force majeure affecting the site.
- **Evaluable patients:** Modified Intent-to-treat patients (mITT) and excluding:
  - Patients lost to follow-up at 18 months (for primary efficacy endpoint and secondary efficacy outcome at 18 month), patients lost to follow-up at 12 months (for secondary efficacy outcome at 12 month), patients lost to follow-up at 6 months (for secondary efficacy outcome at 6 month), except those who were a failure before being lost to follow-up (cf. [Section 7.7](#) for programming rules).
  - Patients with no post-treatment lumbar puncture (i.e. patients who refused all lumbar puncture after treatment and who were not a failure)
  - Patients who died for reasons clearly unrelated to efficacy or safety or disease evolution (\*\*).
  - Early consent withdrawal (before M6, i.e. no planned visit attended after 3-month visit).
- **Per Protocol Set (PPS):** Modified Intent-to-treat patients (mITT) with no major protocol deviations (\*\*\*). Major deviations will be described by patient, and exclusion will be decided during the data review (cf. [Section 8.2](#)).

Notes:

(\*) These patients will be included in the Treated set population as failures.

(\*\*) This will be reviewed during data review meeting (e.g. review of comments and reasons of early discontinuation in end-of-study form).

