#### Best case method (for sensitivity analysis):

The algorithm defined in [Section 10](#) will be used to derive the outcome at 18, 12 and 6 months, with the following changes. The following patients will be considered as **success**:

- Patients lost to follow-up (prior or at visit 18, 12 and 6 months, respectively)
- Patients who refused all post treatment lumbar punctures

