## 8. PLANNED STATISTICAL ANALYSES

### 8.1. Disposition of patients

Disposition of patients and reasons for premature discontinuations of follow-up will be tabulated by cohort (i.e. separating stage 2 patients from stage 1 and intermediate-stage patients), by stage of disease and overall.

- Number of screened HAT positive patients (i.e. patients who gave informed consent)
  - Number and percentage of patients who met all inclusion criteria and no exclusion criteria
  - Number and percentage of patients with at least one inclusion criterion not met and/or exclusion criterion met
- Number of patients not treated, and reasons:
  - Number and percentage of patients with at least one inclusion criterion not met and/or exclusion criterion met
  - Number and percentage of patients not treated due to SAE not related to treatment
  - Number and percentage of patients not treated due to early consent withdrawal or another reason (will be listed)
- Number of patients treated (i.e. who received at least one of the 3 tablets of acoziborole)
- Amongst treated patients:
  - Number and percentage of patients who withdrew from the study prematurely, listed by reason for withdrawal (i.e. death, lost to follow-up, withdrawal of consent, investigator's decision, rescue therapy, other reason)
  - Number and percentage of patients who completed the trial according to the protocol
- The following data will also be provided amongst treated patients:
  - Number and percentage of patients who fled the region due to armed conflict or natural disaster or due to force majeure and for whom no post-treatment data are available (i.e. follow-up visits M3, M6, M12 and M18 not performed).
  - Number and percentage of patients who died for reasons clearly unrelated to the IP or HAT
  - Number and percentage of patients who had at least one minor protocol deviation
  - Number and percentage of patients who had at least one major protocol deviation (an intercurrent post treatment event is not necessarily a major protocol deviation)
  - Number and percentage of patients who underwent lumbar puncture at the end-of-hospitalisation, at the 6-month visit, the 12-month visit and the 18-month visit
  - Number and percentage of patients who attended the end-of-hospitalisation visit, the 3 months visit, the 6-month visit, the 12-month visit and the 18-month visit

In addition, the following data will be provided:

- Date of first patient screened
- Date of first administration of the first patient

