
| Derivation algorithm for stage 1 and intermediate stage (month 18)   | Derivation algorithm for stage 2 (Month 18)  |
|--|--|
| 
Earlier (before M18) unfavorable outcome: increase of WBC in CSF at M6 or M12 with respect to EOH
 
⇒ YES ⇒ 9: Failure (stop)
 
↓
 
NO (no information or no earlier unfavorable assessment)
 
↓
 
Patient has clinical signs or symptoms at M18 evoking a failure
 
⇒ YES ⇒ 10: Failure (stop)
 
↓
 
NO (no clinical signs or symptoms evoking a relapse at M18)
 
↓
 
WBC in CSF ≤ 20 at M12 or absence of LP at M12 and for both cases no increase WBC in CSF at M6 with respect to EOH and no sign and symptoms at M18 evoking a relapse:
 
⇒ YES ⇒ 11: Success (stop) [b]
 
↓
 
NO (at least one criterion not met)
 
↓
 
Patient refused all post treatment lumbar punctures
 
⇒ YES ⇒ 12: Failure (stop) [a,b]
 
↓
 
All other cases ⇒ 13. Failure
 | 
Earlier (before M18) unfavorable outcome: WBC in CSF > 50 at M6 or WBC in CSF > 20 at M12 or increasing between M6 and M12
 
⇒ YES ⇒ 9: Failure (stop)
 
↓
 
NO (no information or no earlier unfavorable assessment)
 
↓
 
Patient has clinical signs or symptoms at M18 evoking a failure
 
⇒ YES ⇒ 10: Failure (stop)
 
↓
 
NO (no clinical signs or symptoms evoking a relapse at M18)
 
↓
 
WBC in CSF ≤ 20 at M12 or in absence of LP at M12 and for both cases WBC in CSF ≤ 50 at M6 and no signs and symptoms at M18 evoking a relapse:
 
⇒ YES ⇒ 11: Success (Stop) [b]
 
↓
 
NO (at least one criterion not met)
 
↓
 
Patient refused all post treatment lumbar punctures
 
⇒ YES ⇒ 12: Failure (Stop) [a,b]
 
↓
 
All other cases ⇒ 13. Failure
 |

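### The Evaluable set's early consent-withdrawal rule drops patients who had already failed, and its lumbar-puncture rule names no visit and is circular

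*SAP*

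**What the plan says.** **Consent withdrawal.** SAP section 5 excludes from the Evaluable set patients described as "Early consent withdrawal (before M6, i.e. no planned visit attended after 3-month visit". Nothing in that bullet refers to earlier failure.

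**The neighbouring rules.** In the same section, the loss-to-follow-up bullet keeps patients who failed before they were lost. The puncture bullet is limited to non-failures: "Patients with no post-treatment lumbar puncture (i.e. patients who refused all lumbar puncture after treatment and who were not a failure". The mITT definition likewise keeps patients who fled the region if a failure (parasite, rescue, death, or more than 50 WBC/µL in CSF at month 6) had been detected early.

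**Status of an early failure.** In the SAP 10.1 algorithm, trypanosomes in any body fluid at any time from dosing to month 18 are a definitive failure at step 3, before follow-up is considered.

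**The puncture rule in the protocol.** Protocol Table 5 defines evaluable patients as those in mITT "for whom at least one lumbar puncture is available (at 6, 12 or 18 months". It also excludes certain deaths and patients who fled. The SAP bullet gives no visits, and SAP section 11 does not list this rewording.

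**Refusal as an outcome.** SAP 6.1, and step 12 of SAP 10.1, make refusal of every post-treatment puncture a failure. The best-case method in SAP 7.6.1 turns into successes "Patients who refused all post treatment lumbar punctures". The last line of the 10.1 algorithm, "All other cases ⇒ 13. Failure", carries no best-case or fair-case flag.

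**Where the set is used.** Sensitivity analysis #2 (SAP 8.6.1.2) repeats the primary analysis on the Evaluable set. SAP 8.6.2 does the same for the secondary efficacy endpoints.

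**The concern.** Sensitivity analysis #2 should show how the success rate looks once patients who cannot be assessed are set aside. A patient with parasites found after dosing has been assessed, and the drug has failed. Whether that patient counts should not depend on which reason for leaving is ticked on the end-of-study form. Protocol 8.1 also keeps data collected before withdrawal in the efficacy analyses, unless the patient refuses. Removing such patients takes failures out of the denominator and never successes, so it can only raise the rate.

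The puncture bullet has a different weakness: two programmers could apply it differently. With no visits named, the term is open. With refusal itself counted as failure, the non-failure condition can be read as cancelling the exclusion.

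This matters more than usual because the plan sets no success criterion. The rate and the lower confidence bound are to be interpreted against historical data, so the supporting analyses carry some of that judgement.

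**Working it through.** **1. One finding, three ways of leaving.** Take a late-stage patient with trypanosomes on Day 11 and no planned visit after month 3.

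| How the patient leaves | mITT outcome (SAP 10.1) | Evaluable set (SAP 5) |
|---|---|---|
| Lost to follow-up | Failure, step 3 | Kept: failed before loss |
| Refuses later punctures | Failure, step 3 | Kept: already a failure |
| Withdraws consent | Failure, step 3 | Removed: no exception |

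**2. The plan's precision figures.** The Jeffreys limits are the 2.5% and 97.5% quantiles of Beta(x + 0.5, n − x + 0.5). With n = 155 (Protocol 9.1):
- x = 138 gives 89.0% (83.4 to 93.2), width 9.8 points, as stated.
- x = 146 gives 94.2% (89.7 to 97.1), width 7.4 points, matching the interval stated for a 94% rate.

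**3. Effect of one withdrawn failure.** The documents give no counts, so one such patient is assumed, with no other exclusions. Dropping one failure changes the rate by x/(n − 1) − x/n = x/[n(n − 1)].
- x = 146: 146/(155 × 154) = 0.0061. The rate becomes 146/154 = 94.8% (90.4 to 97.5) instead of 94.2% (89.7 to 97.1).
- x = 138: 138/(155 × 154) = 0.0058. The rate becomes 138/154 = 89.6% (84.1 to 93.7) instead of 89.0% (83.4 to 93.2).

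Each patient adds about 0.6 points.

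**4. The puncture bullet.** Take a late-stage patient who has the Day 11 puncture, attends every visit without symptoms, and refuses the punctures at months 6, 12 and 18. In SAP 10.1:
- Steps 5 to 8 need a count at month 18 or later.
- Step 9 needs an unfavourable earlier count, and step 10 needs signs or symptoms.
- Step 11 needs a month 6 count of 50 or below.
- The patient therefore ends at step 12, or at step 13 if the Day 11 puncture is taken to count as post-treatment. Both are failures, so the mITT result is the same.

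Evaluable status depends on the reading:
- Day 11 does not count, and refusal is ignored as a ground of failure: excluded, as in Protocol Table 5.
- Day 11 does not count, but refusal is a failure as SAP 6.1 says: the condition is not met and the patient stays. On this reading the bullet removes no late-stage refuser at month 18.
- Day 11 counts: the patient has not refused every puncture and stays.

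If k such refusers are among the 9 failures behind 146/155 (k assumed), the Evaluable rate is 94.2% with them kept. With them excluded it is 94.8% for k = 1, 146/152 = 96.1% (92.0 to 98.3) for k = 3, and 146/150 = 97.3% (93.8 to 99.1) for k = 5. On the literal Day 11 reading the best-case rate is also affected, because step 13 is unflagged. With k = 3 it would be 146/155 = 94.2% instead of 149/155 = 96.1% (92.2 to 98.4).

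**The case against.** **Day 11 is probably not meant.** A reader might infer that the Day 11 puncture counts as post-treatment, because treatment is one dose on Day 1 and "Lumbar puncture will be performed on Day 11, 240 hours after the intake of acoziborole". SAP 8.1 also tabulates an in-hospital puncture beside the later ones: "Number and percentage of patients who underwent lumbar puncture at the end-of-hospitalisation, at the 6-month visit, the 12-month visit and the 18-month visit". But no passage says that it counts, and usage points the other way:
- SAP 8.1 explains missing post-treatment data as the visits at months 3, 6, 12 and 18 not being performed.
- Protocol 2.2.2 uses the puncture phrase after discussing only the punctures at months 6 to 18.
- SAP 10.2 reaches the refusal step from having no puncture at months 6, 12 and 18.
- Protocol 9.10 places the blood and CSF concentration samples at an end-of-treatment visit.

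This stands. The defect is an undefined term, not a rule that keeps these refusers in.

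**The fair-case analysis is not compromised.** Apart from refusers, SAP 7.6.1 resamples patients with no CSF count at the visit and no proven success at another visit. That covers the example patient on either reading.

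**The withdrawal rule is not a departure from the protocol for this patient.** Table 5 requires a puncture at month 6, 12 or 18 and has no failure exception, so it also removes a Day 11 failure who withdraws before month 6. This stands: the fault is inconsistency within the SAP, and Section 11 had nothing to declare on it.

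**Few patients may be affected.** A rescued patient may be recorded under rescue therapy, which SAP 8.1 lists separately from withdrawal of consent. The shift per patient is small beside an interval more than 7 points wide. Both remarks are fair, but no rule guarantees that known failures stay in.

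**Conclusion.** The consent-withdrawal point holds on the text of SAP section 5. One exclusion lacks the protection for known failures that the rules around it have. The error runs in the drug's favour at about 0.6 points per patient, assuming 155 late-stage patients and a success rate near 89% to 94%. The number of such patients is unknown and may be zero.

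The puncture bullet is ambiguous and circular. Its most natural reading agrees with Protocol Table 5, but a strict reading leaves late-stage refusers in as failures and lowers the Evaluable rate. For stage 1 and intermediate patients even the outcome is open, because step 11 of SAP 10.1 does not say what happens when the month 6 count is missing.

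Because the two faults can act in opposite directions, a reader might infer that the Evaluable rate has no clear meaning. The documents do not support that: each fault touches an identifiable and probably small group. Nor do the 4 of 143 NECT patients in SAP 8.6.1.3 without a month 18 assessment measure the size. That figure concerns month 18 only, and such patients can still be successes on earlier counts.

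Only the Evaluable-set analyses are affected, and the best-case analysis on a literal reading. The mITT primary analysis is not.

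**What to change.** 1. In SAP section 5, end the consent-withdrawal bullet with an exception such as: *unless the patient had already failed before withdrawing (trypanosomes, rescue medication, or death related to efficacy, safety or disease evolution)*.
2. Reword the puncture bullet as: *no lumbar puncture at M6, M12, M18 or later, and not a failure on another criterion*. Restoring the Table 5 wording alone would not be enough, because it has no failure exception and would drop early failures without a later puncture.
3. Use the same puncture definition in SAP 6.1, 7.6.1 and 10.1 to 10.3, so that refusers reach the flagged step.

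The cost is SAP wording and minor reprogramming of one analysis set and one algorithm step, with no new data. The downside is that known failures who withdrew re-enter the Evaluable denominator and lower that rate.

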**Table 1 : Classification of patients according to stage/severity at entry**

| Tryps in CSF               | WBC in CSF           |                                 |                      |
|----------------------------|----------------------|---------------------------------|----------------------|
|                            | ≤ 5/ $\mu$ l         | [6-20/ $\mu$ l]                 | > 20/ $\mu$ l        |
| Tryps in CSF (positive)    | Stage 2 (subgroup C) | Stage 2 (subgroup D)            | Stage 2 (subgroup E) |
| No tryps in CSF (negative) | Stage 1 (subgroup A) | Intermediate stage (subgroup B) | Stage 2 (subgroup F) |

**Table 2 : Derivation rules for stage 1, intermediate and stage 2 HAT**

| According to:
Trial FEX004 | According to:
OXA002 Protocol | According to WHO
Clinical trials
recommend...                                       | Trypanosomes
(blood, lymph) | Trypanosomes
in CSF | WBC
in CSF | Subgroups
used in
analyses | HAT stage used
in analyses | HAT cohort used
in analyses |
|-------------------------------|----------------------------------|---|--------------------------------|------------------------|---------------|----------------------------------|-------------------------------|--------------------------------|
| Stage1                        | Early stage                      | Stage 1   | Positive                       | Negative               | AND           | ≤ 5/ $\mu$ l                     | A                             | Stage 1                        |
| Early stage 2                 | Intermediate
stage            | Intermediate stage 2
Not recommended for
clinical trials focused on
second stage | Positive                       | Negative               | AND           | [6-20/ $\mu$ l]                  | B                             | Intermediate
stage          |
| Late stage 2                  | Stage 2                          | Intermediate stage 1
Not recommended for
clinical trials focused on
second stage | Positive                       | Positive               | AND           | ≤ 5 / $\mu$ l                    | C                             | Cohort 1                       |
| Late stage 2                  | Stage 2                          | Intermediate stage 2
Not recommended for
clinical trials focused on
second stage | Positive                       | Positive               | AND           | [6-20/ $\mu$ l]                  | D                             |                                |
| Late stage 2                  | Stage 2                          | Second stage  | Positive                       | Positive               | AND           | > 20 / $\mu$ l                   | E                             |                                |
| Late stage 2                  | Stage 2                          | Second stage  | Positive                       | Negative               | AND           | > 20/ $\mu$ l                    | F                             |                                |

## 6. DEFINITION OF ENDPOINTS

### 6.1. Primary efficacy endpoint

#### Primary endpoint for patients with Stage 2 HAT

The primary endpoint is the outcome (success or failure) at the 18 months visit according to the adapted WHO criteria:

- Success is defined as a cure or a probable cure (cf. algorithm in [Section 10.1](#)).
- Failure is defined as a relapse, probable relapse, death for any reason (up to and including the 18 months visit) or use of rescue medication (up to and including the 18 months visit) or lost to follow-up for any reason (up to and including the 18 months visit) or refusal of all post-treatment lumbar puncture (up to and including the 18 months visit) or had unfavourable outcome earlier than M18 or sign and symptoms evoking a relapse at M18 (cf. algorithm in [Section 10.1](#)).

Note: data review committee composed of those involved in the study conduct and data processing will check before database lock the status of patients (success or failure) using the algorithm presented in [Section 10.1](#).

### 6.2. Secondary efficacy endpoints

#### Endpoint at 6 months in patients with Stage 2 HAT

The response (success or failure) at 6 months in patients with Stage 2 HAT will be derived from the algorithm presented in [Section 10.3](#).

#### Endpoint at 12 months for patient with Stage 2 HAT

The response (success or failure) at 12 months in patients with Stage 2 HAT will be derived from the algorithm presented in [Section 10.2](#).

#### Endpoint at 18 months in Patients with Stage 1 and Intermediate-stage HAT

The response (success or failure) at 18 months in patients with stage 1 and intermediate stage HAT will be derived from the algorithm presented in [Section 10.1](#).

#### Endpoint at 12 months in Patients with Stage 1 and Intermediate-stage HAT

The response (success or failure) at 12 months in patients with stage 1 and intermediate stage HAT will be derived from the algorithm presented in [Section 10.2](#).

#### Endpoint at 6 months in Patients with Stage 1 and Intermediate-stage HAT

The response (success or failure) at 6 months in patients with stage 1 and intermediate stage HAT will be derived from the algorithm presented in [Section 10.3](#).

